Table 40: Summary of Categorical Demographic and Baseline Characteristics by Site - All Enrolled Subjects

Variable	Characteristic	University of Alabama at Birmingham (N = X)		Wake Forest University Health Sciences (N = X)		All Subjects (N=X)	
		n	%	n	%	n	%
Sex	Female	x	xx	x	xx	x	xx
Ethnicity	Not Hispanic or Latino	x	xx	x	xx	x	xx
	Hispanic or Latino	x	xx	x	xx	x	xx
	Not Reported	x	xx	x	xx	x	xx
	Unknown	x	xx	x	xx	x	xx
Race	American Indian or Alaska Native	x	xx	x	xx	x	xx
	Asian	x	xx	x	xx	x	xx
	Native Hawaiian or Other Pacific Islander	x	xx	x	xx	x	xx
	Black or African American	x	xx	x	xx	x	xx
	White	x	xx	x	xx	x	xx
	Multi-Racial	x	xx	x	xx	x	xx
	Unknown	x	xx	x	xx	x	xx

N=Number of subjects enrolled at the specified site.

Table 41: Summary of Categorical Demographic and Baseline Characteristics by Treatment Group - ITT Population

Variable	Characteristic	Amoxicillin (N=X)		Placebo (N=X)		All Subjects (N=X)	
		n	%	n	%	n	%
Sex	Female	x	xx	x	xx	x	xx
Ethnicity	Not Hispanic or Latino	x	xx	x	xx	x	xx
	Hispanic or Latino	x	xx	x	xx	x	xx
	Not Reported	x	xx	x	xx	x	xx
	Unknown	x	xx	x	xx	x	xx
Race	American Indian or Alaska Native	x	xx	x	xx	x	xx
	Asian	x	xx	x	xx	x	xx
	Native Hawaiian or Other Pacific Islander	x	xx	x	xx	x	xx
	Black or African American	x	xx	x	xx	x	xx
	White	x	xx	x	xx	x	xx
	Multi-Racial	x	xx	x	xx	x	xx
	Unknown	x	xx	x	xx	x	xx

N=Number of Subjects in the ITT population randomized to the specified treatment group.

Table 42: Summary of Continuous Demographic and Baseline Characteristics by Site—All Enrolled Subjects

Variable	Statistic	University of Alabama at Birmingham (N = X)	Wake Forest University Health Sciences (N = X)	All Subjects (N=X)
Age	Mean	x.x	x.x	x.x
	Standard Deviation	x.x	x.x	x.x
	Median	x.x	x.x	x.x
	Minimum	x	x	x
	Maximum	x	x	x

Notes: N=Number of subjects enrolled at the specified site.

Table 43: Summary of Continuous Demographic and Baseline Characteristics by Treatment Group - ITT Population

Variable	Statistic	Amoxicillin (N=X)	Placebo (N=X)	All Subjects (N=X)
Age	Mean	x.x	x.x	x.x
	Standard Deviation	x.x	x.x	x.x
	Median	x.x	x.x	x.x
	Minimum	x	x	x
	Maximum	x	x	x

N=Number of subjects in the ITT population randomized to the specified treatment group.

Table 44: Categorical Baseline Sexual History by Treatment Group -ITT Population

Sexual Behavior Category	Value	Amoxicillin (N=X)		Placebo (N=X)		All Subjects (N=X)	
		n	%	n	%	n	%
Has the subject ever douched or used vaginal preparations or drying agents?	No	x	x	x	x	x	x
	Summer's Eve	x	x	x	x	x	x
	Rephresh	x	x	x	x	x	x
	Vagisil	x	x	x	x	x	x
	Other	x	x	x	x	x	x
Does the subjects have a history of recurrent BV (more than one episode of BV in the prior 12 months)?	No	x	x	x	x	x	x
	Yes	x	x	x	x	x	x
Did the subject have a diagnosis of BV within the prior 6 months?	No	x	x	x	x	x	x
	Yes	x	x	x	x	x	x
Subject's most recent sexual partner	Was a new partner	x	x	x	x	x	x
	Was a male	x	x	x	x	x	x
	Used a condom	x	x	x	x	x	x
	N/A	x	x	x	x	x	x
In the last 30 days, how often did the subject use a condom?	Always	x	x	x	x	x	x
	Sometimes	x	x	x	x	x	x
	Never	x	x	x	x	x	x
In the last 3 months, how often did the subject use a condom?	Always	x	x	x	x	x	x
	Sometimes	x	x	x	x	x	x
	Never	x	x	x	x	x	x

N=Number of Subjects in the ITT population.

Treatment group is the treatment to which the subject was randomized.

Screening Visit 0.

Denominator for percentages is the number of subjects with male partners in the specified time frame.

Table 45: Continuous Baseline Sexual History by Treatment Group– ITT Population

Time Frame	Sexual Behavior Characteristic	Statistic	Amoxicillin (N=X)	Placebo (N=X)	All Subjects (N = X)
	Days since the subject last had sexual intercourse	Mean (Standard Deviation)	x.x (x.x)	x.x (x.x)	x.x (x.x)
		Median	x.x	x.x	x.x
		Minimum, Maximum	x, x	x, x	x, x
	Number of episodes of BV in prior 12 months	Mean (Standard Deviation)	x.x (x.x)	x.x (x.x)	x.x (x.x)
		Median	x.x	x.x	x.x
		Minimum, Maximum	x, x	x, x	x, x
In the last 30 days	Number of times the subject douched or used vaginal preparations or drying agents	Mean (Standard Deviation)	x.x (x.x)	x.x (x.x)	x.x (x.x)
		Median	x.x	x.x	x.x
		Minimum, Maximum	x, x	x, x	x, x
	Total number of partners	Mean (Standard Deviation)	x.x (x.x)	x.x (x.x)	x.x (x.x)
		Median	x.x	x.x	x.x
		Minimum, Maximum	x, x	x, x	x, x
	Number of new partners	Mean (Standard Deviation)	x.x (x.x)	x.x (x.x)	x.x (x.x)
		Median	x.x	x.x	x.x
		Minimum, Maximum	x, x	x, x	x, x
	Number of regular partners	Mean (Standard Deviation)	x.x (x.x)	x.x (x.x)	x.x (x.x)
		Median	x.x	x.x	x.x
		Minimum, Maximum	x, x	x, x	x, x
	Number of occasional partners	Mean (Standard Deviation)	x.x (x.x)	x.x (x.x)	x.x (x.x)
		Median	x.x	x.x	x.x
		Minimum, Maximum	x, x	x, x	x, x
	Number of male partners	Mean (Standard Deviation)	x.x (x.x)	x.x (x.x)	x.x (x.x)
		Median	x.x	x.x	x.x
		Minimum, Maximum	x, x	x, x	x, x

Table 45: Continuous Baseline Sexual History by Treatment Group– ITT Population (Continued)

Time Frame	Sexual Behavior Characteristic	Statistic	Amoxicillin (N=X)	Placebo (N=X)	All Subjects (N = X)
In the last 3 months	Total number of partners	Mean (Standard Deviation)	x.x (x.x)	x.x (x.x)	x.x (x.x)
		Median	x.x	x.x	x.x
		Minimum, Maximum	x, x	x, x	x, x
	Number of new partners	Mean (Standard Deviation)	x.x (x.x)	x.x (x.x)	x.x (x.x)
		Median	x.x	x.x	x.x
		Minimum, Maximum	x, x	x, x	x, x
	Number of regular partners	Mean (Standard Deviation)	x.x (x.x)	x.x (x.x)	x.x (x.x)
		Median	x.x	x.x	x.x
		Minimum, Maximum	x, x	x, x	x, x
	Number of occasional partners	Mean (Standard Deviation)	x.x (x.x)	x.x (x.x)	x.x (x.x)
		Median	x.x	x.x	x.x
		Minimum, Maximum	x, x	x, x	x, x
	Number of male partners	Mean (Standard Deviation)	x.x (x.x)	x.x (x.x)	x.x (x.x)
		Median	x.x	x.x	x.x
		Minimum, Maximum	x, x	x, x	x, x

N=Number of Subjects in the ITT population who randomized to the specified treatment group.
Treatment group is the treatment to which the subject was randomized.
Screening Visit 0.

Table 46: Summary of Subjects with Pre-Existing Medical Conditions by MedDRA System Organ Class and Treatment Group - ITT Population – All Sites

MedDRA System Organ Class	Amoxicillin (N=X)		Placebo (N=X)		All Subjects (N=X)	
	n	%	n	%	n	%
Any SOC	x	x	x	x	x	x
[SOC 1]	x	x	x	x	x	x
[SOC 2]	x	x	x	x	x	x

N=Number of subjects in the ITT population who received the specified treatment.

Treatment group is the treatment to which the subject was randomized.

n = Number of subjects reporting medical history within the specified SOC.

A subject is only counted once per SOC.

Tables with Similar Format:

Table 47: Summary of Subjects with Pre-Existing Medical Conditions by MedDRA System Organ Class and Treatment Group - ITT Population – University of Alabama at Birmingham

Table 48: Summary of Subjects with Pre-Existing Medical Conditions by MedDRA System Organ Class and Treatment Group - ITT Population – Wake Forest University Health Sciences

Table 49: Number and Percentage of Subjects with Prior and Concurrent Medications by WHO Drug Classification and Treatment Group - Safety Population - All Subjects

All Subjects (N=X)							
WHO Drug Code Level 1, Anatomic Group	WHO Drug Code Level 2, Therapeutic Subgroup	Amoxicillin (N=X)		Placebo (N=X)		All Subjects (N=X)	
		n	%	n	%	n	%
Any Level 1 Codes	Any Level 2 Codes	x	x	x	x	x	x
[ATC Level 1 - 1]	Any	x	x	x	x	x	x
	[ATC 2 - 1]	x	x	x	x	x	x
	[ATC 2 - 2]	x	x	x	x	x	x
	[ATC 2 - 3]	x	x	x	x	x	x
[ATC Level 1 - 2]	Any	x	x	x	x	x	x
	[ATC 2 - 1]	x	x	x	x	x	x
	[ATC 2 - 2]	x	x	x	x	x	x
	[ATC 2 - 3]	x	x	x	x	x	x

N= Number of subjects in the Safety population who received the specified treatment.
n=Number of subjects reporting taking at least one medication in the specific WHO Drug Class.

Tables with Similar Format:

Table 50: Number and Percentage of Subjects with Prior and Concurrent Medications by WHO Drug Classification and Treatment Group - Safety Population - University of Alabama at Birmingham

Table 51: Number and Percentage of Subjects with Prior and Concurrent Medications by WHO Drug Classification and Treatment Group - Safety Population - Wake Forest University Health Sciences

Table 52: Proportion of Subjects Reporting Treatment Related Adverse Events Following the First Dose of Treatment through Visit 2 by Treatment Group – Safety Population

Treatment Group	Number of Subjects with AEs n	Number of Subjects N	Proportion of Subjects with AEs	Proportion of Subjects with AEs 95% CI	Difference in Proportion of Subjects with AEs between Amoxicillin and Placebo	Difference in Proportion of Subjects with AEs between Amoxicillin and Placebo 95% CI	P-value
Amoxicillin	x	x	0.xx	0.xx, 0.xx	0.xx	0.xx, 0.xx	0.xxx
Placebo	x	x	0.xx	0.xx, 0.xx	--	--	--
All Subjects	x	x	0.xx	0.xx, 0.xx	--	--	--

The denominator for proportions is based on the number of subjects who received the specified treatment.

95% CI = 95% Blaker confidence interval.

P-value from the Fisher’s exact two-sided test at the .05 level of significance.

Table 53: Proportion of Subjects Discontinuing Treatment Early Due to Adverse Events by Treatment Group – Safety Population

Treatment Group	Number of Subjects with AEs n	Number of Subjects N	Proportion of Subjects Discontinuing Early due to AEs	Proportion of Subjects Discontinuing Early due to AEs 95% CI	Difference in Proportion of Subjects Discontinuing Early due to AEs between Amoxicillin and Placebo	Difference in Proportion of Subjects Discontinuing Early due to AEs between Amoxicillin and Placebo 95% CI	P-value
Amoxicillin	x	x	0.xx	0.xx, 0.xx	0.xx	0.xx, 0.xx	0.xxx
Placebo	x	x	0.xx	0.xx, 0.xx	--	--	--
All Subjects	x	x	0.xx	0.xx, 0.xx	--	--	--

The denominator for proportions is based on the number of subjects who received the specified treatment.

95% CI = 95% Blaker confidence interval.

P-value from the Fisher’s exact two-sided test at the .05 level of significance.

Table 54: Number and Percentage of Subjects Experiencing Unsolicited Adverse Events with 95% Confidence Intervals by MedDRA System Organ Class and Preferred Term, and Treatment Group - Safety Population

MedDRA System Organ Class	MedDRA Preferred Term	Amoxicillin (N=X)				Placebo (N=X)				All Subjects (N=X)			
		n	%	95% CI	Events	n	%	95% CI	Events	n	%	95% CI	Events
Any SOC	Any PT	x	x	x, x	x	x	x	x, x	x	x	x	x, x	x
[SOC 1]	Any PT	x	x	x, x	x	x	x	x, x	x	x	x	x, x	x
	[PT 1]	x	x	x, x	x	x	x	x, x	x	x	x	x, x	x
	[PT 2]	x	x	x, x	x	x	x	x, x	x	x	x	x, x	x
[SOC 2]	Any PT	x	x	x, x	x	x	x	x, x	x	x	x	x, x	x
	[PT 1]	x	x	x, x	x	x	x	x, x	x	x	x	x, x	x
	[PT 2]	x	x	x, x	x	x	x	x, x	x	x	x	x, x	x

N = Number of subjects in the Safety Analysis Population who received the specified treatment.

95% CI = 95% Blaker confidence interval.

This table presents number and percentage of subjects.

A subject is only counted once per PT/timepoint.

Table 55: Number and Percentage of Subjects Experiencing Unsolicited Adverse Events by MedDRA System Organ Class and Preferred Term, Maximum Severity and Relationship - Safety Population

			All Subjects (N = X)					
			Related		Not Related		Total	
			n	%	n	%	n	%
Any SOC	Any PT	Any Severity	x	x	x	x	x	x
		Mild	x	x	x	x	x	x
		Moderate	x	x	x	x	x	x
		Severe	x	x	x	x	x	x
[SOC 1]	Any PT	Any Severity	x	x	x	x	x	x
		Mild	x	x	x	x	x	x
		Moderate	x	x	x	x	x	x
		Severe	x	x	x	x	x	x
	[PT 1]	Any Severity	x	x	x	x	x	x
		Mild	x	x	x	x	x	x
		Moderate	x	x	x	x	x	x
		Severe	x	x	x	x	x	x

N = Number of subjects in the Safety Analysis Population

This table presents number and percentage of subjects as well as number of events.

For severity, a subject is counted once per preferred term and is summarized according to their highest severity.

Table 56: Number and Percentage of Subjects Experiencing Unsolicited Adverse Events by MedDRA System Organ Class and Preferred Term, Maximum Severity, Relationship, and Treatment Group - Safety Population

			Amoxicillin (N = X)						Placebo (N = X)					
			Related		Not Related		Total		Related		Not Related		Total	
			n	%	n	%	n	%	n	%	n	%	n	%
Any SOC	Any PT	Any Severity	x	x	x	x	x	x	x	x	x	x	x	x
		Mild	x	x	x	x	x	x	x	x	x	x	x	x
		Moderate	x	x	x	x	x	x	x	x	x	x	x	x
		Severe	x	x	x	x	x	x	x	x	x	x	x	x
[SOC 1]	Any PT	Any Severity	x	x	x	x	x	x	x	x	x	x	x	x
		Mild	x	x	x	x	x	x	x	x	x	x	x	x
		Moderate	x	x	x	x	x	x	x	x	x	x	x	x
		Severe	x	x	x	x	x	x	x	x	x	x	x	x
	[PT 1]	Any Severity	x	x	x	x	x	x	x	x	x	x	x	x
		Mild	x	x	x	x	x	x	x	x	x	x	x	x
		Moderate	x	x	x	x	x	x	x	x	x	x	x	x
		Severe	x	x	x	x	x	x	x	x	x	x	x	x

N = Number of subjects in the Safety Analysis Population who received the specified treatment.

This table presents number and percentage of subjects as well as number of events.

For severity, a subject is counted once per preferred term and is summarized according to their highest severity.

Table 57: Adverse Events Occurring in 5% of Subjects in Any Treatment Group by MedDRA System Organ Class, Preferred Term, and Treatment Group - Safety Population

Preferred Term	MedDRA System Organ Class	Amoxicillin (N=X)			Placebo (N=X)			All Subjects (N=X)		
		n	%	Events	n	%	Events	n	%	Events
Serious Adverse Events										
All	All	x	x	x	x	x	x	x	x	x
PT1	SOC1	x	x	x	x	x	x	x	x	x
Etc.	Etc.	x	x	x	x	x	x	x	x	x
Non-serious Adverse Events										
All	All	x	x	x	x	x	x	x	x	x
PT1	SOC1	x	x	x	x	x	x	x	x	x
Etc	Etc	x	x	x	x	x	x	x	x	x

N = number of subjects in the Safety Population who received the specified treatment.

n= number of subjects reporting event.

This table presents number and percentage of subjects as well as number of events.

Table 58: Listing of Non-Serious, Unsolicited, Moderate or Severe Adverse Events

Adverse Event	Study Day	Severity	Relationship to Study Treatment	In Not Related, Alternative Etiology	Action Taken with Study Treatment	Subject Discontinued Due to AE	Outcome	MedDRA System Organ Class	MedDRA Preferred Term
Subject ID: , Treatment Group: , AE Number:									
xxxxxxx	xx	xxxxxx	xxxxxx	xxxxx	xxxxxx	Y/N	xxxxx	xxxxx	xxxxx
Comments:xxxxxxxxxx									
Subject ID: , Treatment Group: , AE Number:									
xxxxxxx	xx	xxxxxx	xxxxxx	xxxxx	xxxxxx	Y/N	xxxxx	xxxxx	xxxxx
Comments:xxxxxxxxxx									

Table 59: Listing of Serious Adverse Events

Adverse Event	Study Day the Event Became Serious	Reason Reported as an SAE	Severity	Relationship to Study Treatment	In Not Related, Alternative Etiology	Action Taken with Study Treatment	Subject Discontinued Due to AE	Outcome	MedDRA System Organ Class	MedDRA Preferred Term
Subject ID: , Treatment Group: , AE Number:										
xxxxxxx	xx	xxxxxx	xxxxxx	xxxxxx	xxxxxx	xxxxxx	Y/N	xxxxx	xxxxx	xxxxx
Comments: xxxxxxxxxxxxxxx										
Subject ID: , Treatment Group: , AE Number:										
xxxxxxx	xx	xxxxxx	xxxxxx	xxxxxx	xxxxxx	xxxxxx	Y/N	xxxxx	xxxxx	xxxxx
Comments: xxxxxxxxxxxxxxx										

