5. SAMPLE SIZE CONSIDERATIONS

Sample size calculations were based on detecting a decrease in GV colonization rate from 80% among participants receiving placebo to as large as 44% among participants receiving amoxicillin. Using the two-sided Pearson Chi-Square test with Yates continuity correction, significance level of 0.05, and assuming an amoxicillin to placebo allocation ratio of 1:1, 82 women (41 in each arm) would provide 90% power to detect a difference in colonization rates of 36% (i.e. 44% colonization rate in the amoxicillin arm).

Assuming a 15% drop-out rate between enrollment and the TOC visit approximately 98 women will need to be randomized to obtain 82 women evaluable for the primary analysis. Assuming 40% of women without BV will have a positive NAAT test for GV at screening, approximately 245 women without BV will need to be screened to randomize 98 women in the study.

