6. GENERAL STATISTICAL CONSIDERATIONS

6.1. General Principles

Tabulations will be used extensively to summarize the data. All continuous variables will be summarized using the following descriptive statistics: n (sample size), mean, standard deviation, median, maximum and minimum. The frequency and percentages (based on the sample size) of observed levels will be reported for all categorical measures. Wilson confidence intervals for binomial proportions and differences in binomial proportions will be computed for efficacy variables. Blaker confidence intervals for binomial proportions and differences in binomial proportions will be computed for safety variables. For the hypothesis tests comparing treatment groups with respect to safety outcomes, the two-sided Fisher's Exact test will be used. For the hypothesis tests comparing treatment groups with respect to efficacy outcomes, the two-sided Pearson Chi-Square test with Yates continuity correction will be used. For all tests, a 5% two-sided significance level will be used.

For all efficacy outcome measures, the Intention-to-Treat (ITT) population (see Section 6.3) will be used as the primary analysis population and the Per Protocol population will be used as a secondary analysis population. For all safety analyses, the Safety population will be used as the analysis population.

All summary tables will be structured with a column/sub-table for each treatment group (Amoxicillin, Placebo, and All Subjects). In general, all data will be listed by treatment group and/or subject, and when appropriate by visit number within subject. The total population size relevant to that table/column if applicable, including any missing observations will be displayed in the tables.

Note that in the data listings, Subject ID is the unique subject identifier, not the Study ID used on study and dates will not be included, only Study Day.

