8.3. Exploratory Efficacy Analyses

A summary of Amsel criteria is provided for subjects by visit and treatment group for each analysis population in Table 12 and Table 13. The number of Amsel criteria present (0,1,2,3), pH (> 4.5 , ≤ 4.5), Clue cells ($\geq 20\%$, $< 20\%$), and Amine ("whiff") test on KOH wet mount (Positive, Negative) will be summarized. A summary of Amsel criteria is provided for subjects by treatment group and GV eradication status at Visit 2 for subjects in the ITT population and PP population (Table 14 and Table 15). GV eradication status is categorized as "GV Eradicated," "GV Not Eradicated," "Not Evaluable." See Section 3.3 for the definition of evaluable. A subject listing of individual Amsel criteria will be provided in Listing 6.

Table 16 and Table 17 presents the proportion of subjects with Nugent score of 3 or less (normal), 4-6 (intermediate), and 7-10 (BV) in each treatment group at Screening and at Visit 2 (Day 15-21). Continuous Nugent scores will also be presented by analysis population, study visit, and treatment group in Table 18 and Table 19. A subject listing of Nugent scores will be presented in Listing 6. Raw Nugent scores are displayed graphically by visit, treatment group, and analysis population in Figure 2 and Figure 3. Categorical and Continuous Nugent Score characteristics at Visit 2 are presented by GV eradication status, and treatment group for subjects in the ITT population and PP population (Table 20, Table 21, Table 22 and Table 23).

The mean count of *Lactobacillus spp.*, *Gardnerella/Bacteroides spp.*, and *Mobiluncus spp.*, respectively, in each treatment group at Screening and at Visit 2 (Day 15-21). Mean count and standard deviation of each specimen type will be presented by study visit, analysis population, and treatment group. Additionally, mean change from baseline and corresponding standard deviation will be presented for Visit 2. See Table 24 and Table 25. Mean count and standard deviation of *Lactobacillus spp.*, *Gardnerella/Bacteroides spp.*, and *Mobiluncus spp.* at Visit 2 is presented by GV eradication status for subjects in the ITT population and PP population (Table 26 and Table 27).

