Implementation Note: Change footnote from “Treatment group is the treatment to which the subject was randomized.” to “Treatment group is the actual treatment received”

Table 14: Amsel Criteria at Visit 2 by GV Eradication Status and Treatment Group - ITT Population

Amsel Criteria		Amoxicillin (N=X)						Placebo (N=X)						All Subjects (N=X)					
		GV Eradicated (N=X)		GV Not Eradicated (N=X)		Not Evaluable (N=X)		GV Eradicated (N=X)		GV Not Eradicated (N=X)		Not Evaluable (N=X)		GV Eradicated (N=X)		GV Not Eradicated (N=X)		Not Evaluable (N=X)	
		n	%	n	%	n	%	n	%	n	%	n	%	n	%	n	%	n	%
Number of Amsel Criteria Present	0/3	x	x	x	x	x	x	x	x	x	x	x	x	x	x	x	x	x	x
	1/3	x	x	x	x	x	x	x	x	x	x	x	x	x	x	x	x	x	x
	2/3	x	x	x	x	x	x	x	x	x	x	x	x	x	x	x	x	x	x
	3/3	x	x	x	x	x	x	x	x	x	x	x	x	x	x	x	x	x	x
Vaginal pH	>4.5	x	x	x	x	x	x	x	x	x	x	x	x	x	x	x	x	x	x
	≤4.5	x	x	x	x	x	x	x	x	x	x	x	x	x	x	x	x	x	x
Clue Cells	≥20%	x	x	x	x	x	x	x	x	x	x	x	x	x	x	x	x	x	x
	<20%	x	x	x	x	x	x	x	x	x	x	x	x	x	x	x	x	x	x
Whiff Test	Positive	x	x	x	x	x	x	x	x	x	x	x	x	x	x	x	x	x	x
	Negative	x	x	x	x	x	x	x	x	x	x	x	x	x	x	x	x	x	x

Denominator for percentages is the number of subjects who received the specified treatment.
Treatment group is the treatment to which the subject was randomized.

Tables with Similar Format:

Table 15: Amsel Criteria at Visit 2 by GV Eradication Status and Treatment Group - PP Population

Implementation Note:

1. Change footnote from “Treatment group is the treatment to which the subject was randomized.” to “Treatment group is the actual treatment received.”
2. No “Not Evaluable” Column for PP Population.

Table 16: Nugent Scores by Category, Study Visit, and Treatment Group - ITT Population

	Amoxicillin (N=X)				Placebo (N=X)				All Subjects (N=X)			
	Screening Visit (N = X)		Visit 2 (N = X)		Screening Visit (N = X)		Visit 2 (N = X)		Screening Visit (N = X)		Visit 2 (N = X)	
	n	%	n	%	n	%	n	%	n	%	n	%
0-3 (Normal)	x	x	x	x	x	x	x	x	x	x	x	x
4-6 (Intermediate)	x	x	x	x	x	x	x	x	x	x	x	x
7-10 (BV)	x	x	x	x	x	x	x	x	x	x	x	x

Denominator for percentages is the number of subjects who received the specified treatment.
Treatment group is the treatment to which the subject was randomized.

Tables with similar format:

Table 17: Nugent Scores by Category, Study Visit, and Treatment Group - PP Population

Implementation Note: Change footnote from “Treatment group is the treatment to which the subject was randomized.” To “Treatment group is the actual treatment received.”

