Table 18: Continuous Nugent Score Characteristics by Study Visit, and Treatment Group - ITT Population

Statistic	Amoxicillin (N=X)		Placebo (N=X)		All Subjects (N=X)	
	Screening Visit (N = X)	Visit 2 (N = X)	Screening Visit (N = X)	Visit 2 (N = X)	Screening Visit (N = X)	Visit 2 (N = X)
Mean	x.x	x.x	x.x	x.x	x.x	x.x
Standard Deviation of Mean	x.x	x.x	x.x	x.x	x.x	x.x
Mean Change from Visit 1	--	x.x	--	x.x	--	x.x
Standard Deviation of Mean Change from Visit 1	--	x.x	--	x.x	--	x.x

Treatment group is the treatment to which the subject was randomized.

Tables with similar format:

Table 19: Continuous Nugent Score Characteristics by Study Visit, and Treatment Group - PP Population

Implementation Note: Change footnote from “Treatment group is the treatment to which the subject was randomized.” to “Treatment group is the actual treatment received.”

Table 20: Nugent Scores at Visit 2 by Category, GV Eradication Status, and Treatment Group - ITT Population

Nugent Score Category	Amoxicillin (N=X)						Placebo (N=X)						All Subjects (N = X)					
	GV Eradicated (N = X)		GV Not Eradicated (N = X)		Not Evaluable (N = X)		GV Eradicated (N = X)		GV Not Eradicated (N = X)		Not Evaluable (N = X)		GV Eradicated (N = X)		GV Not Eradicated (N = X)		Not Evaluable (N = X)	
	n	%	n	%	n	%	n	%	n	%	n	%	n	%	n	%	n	%
0-3 (Normal)	x	x	x	x	x	x	x	x	x	x	x	x	x	x	x	x	x	x
4-6 (Intermediate)	x	x	x	x	x	x	x	x	x	x	x	x	x	x	x	x	x	x
7-10 (BV)	x	x	x	x	x	x	x	x	x	x	x	x	x	x	x	x	x	x

Denominator for percentages is the number of subjects in the ITT population for each treatment group.
Treatment group is the treatment to which the subject was randomized.

Tables with similar format:

Table 21: Nugent Scores at Visit 2 by Category, GV Eradication Status, and Treatment Group - PP Population

Implementation Note:

1. Change footnote from “Treatment group is the treatment to which the subject was randomized.” to “Treatment group is the actual treatment received.”
2. No “Not Evaluable” Column for PP Population.

Table 22: Continuous Nugent Score Characteristics at Visit 2 by GV Eradication Status and Treatment Group - ITT Population

Statistic	Amoxicillin (N=X)			Placebo (N=X)			All Subjects (N = X)		
	GV Eradicated (N = X)	GV Not Eradicated (N = X)	Not Evaluable (N = X)	GV Eradicated (N = X)	GV Not Eradicated (N = X)	Not Evaluable (N = X)	GV Eradicated (N = X)	GV Not Eradicated (N = X)	Not Evaluable (N = X)
Mean	x.x	x.x	x.x	x.x	x.x	x.x	x.x	x.x	x.x

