		Minimum, Maximum	x, x	x, x
	Number of regular partners	Mean (Standard Deviation)	x.x (x.x)	x.x (x.x)
		Median	x.x	x.x
		Minimum, Maximum	x, x	x, x
	Number of occasional partners	Mean (Standard Deviation)	x.x (x.x)	x.x (x.x)
		Median	x.x	x.x
		Minimum, Maximum	x, x	x, x
	Number of male partners	Mean (Standard Deviation)	x.x (x.x)	x.x (x.x)
		Median	x.x	x.x
		Minimum, Maximum	x, x	x, x

N = Number of subjects in the NAAT Screening Population within the specified GV status category. Screening Visit 0.

Table 32: Categorical Baseline Sexual History by Visit 2 BV Status - ITT Population – Amoxicillin Treatment Group

Amoxicillin (N=X)									
Sexual Behavior Category	Value	BV by Amsel Criteria (N=X)		BV by Nugent Score (N=X)		BV by Amsel Criteria and Nugent Score (N=X)		No BV by either Amsel or Nugent Score (N=X)	
		n	%	n	%	n	%	n	%
Has the subject ever douched or used vaginal preparations or drying agents?	No	x	x	x	x	x	x	x	x
	Summer’s Eve	x	x	x	x	x	x	x	x
	Rephresh	x	x	x	x	x	x	x	x
	Vagisil	x	x	x	x	x	x	x	x
	Other	x	x	x	x	x	x	x	x
Does the subjects have a history of recurrent BV (more than one episode of BV in the prior 12 months)?	No	x	x	x	x	x	x	x	x
	Yes	x	x	x	x	x	x	x	x
Did the subject have a diagnosis of BV within the prior 6 months?	No	x	x	x	x	x	x	x	x
	Yes	x	x	x	x	x	x	x	x
Subject’s most recent sexual partner	Was a new partner	x	x	x	x	x	x	x	x
	Was a male	x	x	x	x	x	x	x	x
	Used a condom	x	x	x	x	x	x	x	x
	N/A	x	x	x	x	x	x	x	x
In the last 30 days, how often did the subject use a condom?	Always	x	x	x	x	x	x	x	x
	Sometimes	x	x	x	x	x	x	x	x
	Never	x	x	x	x	x	x	x	x
In the last 3 months, how often did the subject use a condom?	Always	x	x	x	x	x	x	x	x
	Sometimes	x	x	x	x	x	x	x	x
	Never	x	x	x	x	x	x	x	x

N=Number of subjects in the ITT population who received the specified treatment and has the specified BV status.
 Denominator for percentages is the number of subjects in the Amoxicillin group (N) within the specified BV Status category.
 Treatment group is the treatment to which the subject was randomized.
 Screening Visit 0.
 Denominator for percentages is the number of subjects in the Amoxicillin group with male partners in the specified time frame.

Table with similar format:

Table 33: Categorical Baseline Sexual History by Visit 2 BV Status - ITT Population – Placebo Treatment Group

Table 34: Continuous Baseline Sexual History by Visit 2 BV Status - ITT Population – Amoxicillin Treatment Group

Amoxicillin (N=X)						

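### SAP Tables 14, 15, 20 and 21 divide by the whole treatment arm inside GV-eradication-status columns, so their percentages reflect group size as well as BV frequency

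*SAP*

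**What the plan says.** SAP Section 8.3 plans summaries of Visit 2 Amsel criteria and Nugent category by treatment group and GV eradication status, with three status categories. The shells are titled "Table 14: Amsel Criteria at Visit 2 by GV Eradication Status and Treatment Group - ITT Population" and "Table 20: Nugent Scores at Visit 2 by Category, GV Eradication Status, and Treatment Group - ITT Population". In both, every status column within each arm has its own N in the header.

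The denominator footnotes are:

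- **Table 20:** "Denominator for percentages is the number of subjects in the ITT population for each treatment group".
- **Table 14:** "Denominator for percentages is the number of subjects who received the specified treatment".

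Tables 15 and 21 are the per-protocol versions in the same format. Their implementation notes change the treatment-group sentence and remove the Not Evaluable column. They leave the denominator sentence alone.

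SAP Section 6.1 gives only a general rule: "The frequency and percentages (based on the sample size) of observed levels will be reported for all categorical measures". It does not say which sample size applies in a table with nested columns. Table 32, which is also split by a Visit 2 status, does say: "Denominator for percentages is the number of subjects in the Amoxicillin group (N) within the specified BV Status category". (Table 32 has a second denominator note about women with male partners; neither of its notes uses the whole arm.)

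**The concern.** A table laid out this way invites one question: among women whose GV was eradicated, what share have BV or a given Amsel finding, and how does that compare with women still positive? The answer needs the column N as denominator. With the arm as denominator, each cell is the share of the arm that is both in that status group and in that Nugent or Amsel category. A small group then shows small percentages in every row, whatever its BV frequency.

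The trial expects very unequal groups on placebo, so the distortion is largest there. There are also two inconsistencies between the footnotes and the populations. Tables 14 and 20 are both ITT tables, yet one divides by women treated and the other by all ITT women. Table 21 is a PP table that, as written, would divide by the ITT arm.

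**Working it through.** **Inputs.** SAP Section 5 (same text in Protocol Section 11.2) gives GV colonization of 80% on placebo and 44% on amoxicillin, 41 evaluable women per arm, 90% power, 15% drop-out and 98 randomized. The plan gives no BV rate at Visit 2, so every BV rate below is an assumption.

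**Reproducing the plan's figures.** Exact power of the two-sided Yates-corrected test with 41 per arm at 20% v 56% eradication is 90.3%. The continuity-corrected sample-size formula gives 42 per arm, within rounding of 41. For drop-out, 41/0.85 = 48.2, so 49 per arm and 98 in total. These figures are sound and can be used to size the columns.

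**Planned column sizes** (49 per arm, 41 with a result, 49 − 41 = 8 without):

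| Arm | Eradicated | Not eradicated | Not evaluable |
|---|---|---|---|
| Amoxicillin | 41 × 0.56 ≈ 23 | 41 − 23 = 18 | 8 |
| Placebo | 41 × 0.20 ≈ 8 | 41 − 8 = 33 | 8 |

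**What each column sums to.** With the arm N as denominator, the Nugent rows of a status column add up to (column n)/49 if all its women have a score:

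- Amoxicillin: 23/49 = 47% eradicated, 18/49 = 37% not eradicated.
- Placebo: 8/49 = 16% eradicated, 33/49 = 67% not eradicated.

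**No true association.** Assume BV in 15% of every group. The printed percentage is 0.15 × (column n)/49:

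- Placebo: 0.15 × 8/49 = 2.4% v 0.15 × 33/49 = 10.1%.
- Amoxicillin: 0.15 × 23/49 = 7.0% v 0.15 × 18/49 = 5.5%.

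The placebo contrast is about fourfold and comes entirely from group size.

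**When the order reverses.** Within an arm, printed ratio = (true BV rate ratio) × (ratio of column sizes). If the smaller group has the higher BV rate, the order reverses when the true rate ratio lies between 1 and (larger n)/(smaller n):

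- Placebo: limit 33/8 ≈ 4.1. Here the eradicated group would have to have the higher BV rate.
- Amoxicillin: limit 23/18 ≈ 1.3. Here the non-eradicated group would have to have the higher BV rate.
- Between arms, within the GV Eradicated column: limit 23/8 ≈ 2.9.

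With 0 to 8 women missing per arm, the within-arm limits range over 3.9–4.1 and 1.2–1.3.

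**Illustration with assumed counts on placebo.** Take BV in 2 of 8 eradicated and 6 of 33 not eradicated. The column N gives 25.0% v 18.2%. The arm N gives 2/49 = 4.1% v 6/49 = 12.2%.

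**The case against.** Joint percentages are a legitimate way to show a cross-tabulation, and the shells print n and a column N, so a careful reader can recover the conditional percentage by one division. The Table 14 wording matches that of Tables 12 and 16, which suggests a carried-over footnote more than a deliberate choice. The tables are descriptive, with no test or decision rule attached. All of this stands and limits the weight of the point. It does not make the printed percentages suitable for comparing columns, which is what the layout invites.

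Three stronger readings are tempting and are not supported.

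- **That the tables will reverse the comparison.** This depends on BV rates the plan does not give. On placebo it needs BV to be commoner after eradication, which runs against the plan's own rationale. If BV is commoner in women still positive, the placebo columns keep the right order and exaggerate the gap. On amoxicillin, reversal needs rates within a ratio of about 1.3.
- **That these tables are the plan's only link between eradication and flora, or that the next study rests on them.** Tables 22–23 (continuous Nugent score) and 26–27 (morphotype counts) are also split by eradication status and use no percentages, and Listing 6 gives the individual data. Protocol Section 2.2 and SAP Section 4.2 make the next step depend on whether amoxicillin eradicates GV, which is the primary analysis.
- **That Tables 12, 13, 16 and 17 share the fault.** They are not split by eradication status. Keeping the whole arm in an ITT denominator is a recognised convention, and equal drop-out would scale both arms alike.

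**Conclusion.** The point holds as a footnote error in four exploratory tables. Table 20 states a whole-arm denominator without ambiguity, Table 14 does so in substance, and Tables 15 and 21 inherit the wording. Section 6.1 does not override it, and Table 32 shows that the SAP uses the status-category N elsewhere.

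At the planned eradication rates, with 49 randomized and 41 evaluable per arm, equal BV rates assumed at 15% would print as about 2.4% v 10.1% on placebo and 7.0% v 5.5% on amoxicillin. The split of the columns rests on the plan's own assumptions; the 15% is only illustrative, but the placebo ratio of about 4.1 would be the same at any common rate. The primary analysis (Tables 10 and 11) is untouched, so this is a minor correction.

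**What to change.** In Tables 14, 15, 20 and 21, replace the denominator footnote with one that uses the number of women in that arm and eradication-status column who have a non-missing Visit 2 result for the item tabulated (Amsel or Nugent). In Tables 15 and 21, add to the implementation notes that the denominator is drawn from the PP population.

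A related clarification is worth making in the same edit, because it decides who is counted in each column. SAP Section 6.5 classes a missing Visit 2 GV NAAT as treatment failure in the ITT population, while Section 8.3 provides a Not Evaluable category. State which column those women enter in Tables 14 and 20.

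The cost is a few sentences in the shells and a changed denominator in the programs for four tables. No new data, rows or columns are needed.
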